In summary, the behavioral component of the proposed multi-modal treatment will be a PILI that targets improvements in spoken language and challenging behavior for 10- to 17-year-olds with FXS by increasing PVR within picture-book based storytelling episodes. Finally, parents/caregivers will be encouraged to use the targeted strategies in other everyday interactions with their child. The intervention will be delivered to parents/caregivers in their homes by way of VTC. Considerable preliminary work will need to be conducted, however, before combining it with lovastatin. Thus, we propose to spend the first 18 months of the project conducting two small-scale studies of PILI alone. The first phase (Phase 1) of the PILI study was designed to collect preliminary data, enrolled three mothers and their sons and will be completed by end of December 2014. NIH has requested that we continue to test the preliminary efficacy of the behavioral intervention using a small N group design study prior to implementing the phase of the intervention which includes the drug Thus, the second phase of the study (Phase 2) will be a group design (N=30) with randomized assignment to a Treatment Group or a Wait List Comparison Group. Participants in the Treatment Group receive the behavioral intervention and the Wait List Comparison Group receives treatment as usual. The final phase of the study (Phase3) will be a clinical trial (N=50) in which participants are randomly assigned to receive the behavioral intervention alone or in combination with Lovastatin.

5) Inclusion and Exclusion Criteria

Subjects will be screened initially through a pre-screening form either over the phone or in person at the MIND Institute. If the subject is eligible based on the responses to the pre-screening form they will be given the option of scheduling a screening visit to complete screening assessments and confirm if language level and overall functioning are adequate to participate in the trial.

Inclusion Criteria:

- 1. Documentation of a full mutation with absence or deficient FMRP levels.
- 2. Males and females ages 10 through 17 years (Consent Forms A and B). Note:

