- 3. Changes in behavioral therapy or educational programming during the study. This does not include scheduled school holidays.
- 4. Have any disease or condition (medical or surgical) at screening that might compromise the hematologic, cardiovascular, pulmonary, renal, gastrointestinal, or hepatic systems; or other conditions that might interfere with the absorption, distribution, metabolism, or excretion of the investigational product, or would place the subject at increased risk.
- 5. Patients who, in the opinion of the investigator, are unsuitable in any other way to participate in this study, including being unable to comply with the requirements of the study or displaying clinically significant abnormalities in safety assessments at screening.
- 6. Patients on prohibited medications (see package insert for more information):
 - a. Potent inhibitors of CYP3A4 (itraconazole, ketoconazole, posaconazole, voriconazole, HIV protease inhibitors, boceprevir, telaprevir, erythromycin, clarithromycin, telithromycin, and nefazodone)
 - b. Gemfibrozil
 - c. Other lipid-lowering drugs
 - d. Cyclosporine
 - e. Danazol, diltiazem, dronedarone, or verapamil
 - f. Amiodarone
 - g. Colchicine
 - h. Ranolazine
 - *i.* Coumarin anticoagulants
 - j. mGluR5 antagonists
- 7. History of recurrent status epilepticus.
- 8. Inability to withhold grapefruit and grapefruit juice from diet during the entire clinical trial.

- 9. Subjects unwilling to abstain from alcoholic beverages during the trial
- 10. Subjects who are actively suicidal.

6) Number of Subjects

We hope to enroll up to 113 participants through the entire study under the 4 consent form versions. Consent form A will be utilized to enroll up to 30 subjects and their mothers. Consent form B will be utilized to enroll up to 50 subjects and their mothers/caregivers into the clinical trial portion of the study. Up to 30 additional pilot participants may be recruited from ongoing studies here at the MIND using Consent form C. Mothers of the pilot participants enrolled under consent form C will not be involved in the clinician-child interactions. We will also recruit 3 boys with FXS between the ages of 5- and 8-years old to participate in a downward extension of the study utilizing Consent form D. This brings the total number of potential participants to 113.

7) Recruitment Methods

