Once eligibility is confirmed, subjects will be approached to obtain their authorization to access and use their health information for the research. Please see Section 14 for additional information regarding Data Management and Confidentiality.

8) Compensation to the Subjects

Subjects will not be compensated for their participation. Possible expenses to the subject's family include time spent at the clinic as well as expenses for travelling. Therefore subjects who would otherwise not be able to participate may be eligible for travel reimbursement for travel costs incurred as specified in question 25.

9) Study Timelines

We anticipate seeing 30 pilot participants in the first 18 months under consent form C. During this same time period up to an additional thirty participants and their mothers will be seen under consent form A, phases 1 and 2 of the study. During Phase 3, 50 participants and their parent/caregiver will be recruited into the clinical trial portion utilizing consent form B. In addition, 3 subjects will be recruited into phase 4, under consent form D. Phases 2,3, and 4 of the study, using consent forms A, B and D, will occur over the last 3.5 years of the project).

10) Study Endpoints

The primary outcome measure is a spoken language composite measured at baseline and at the end of treatment. Comparison of the two treatment groups on the outcome measure will be made through analysis of covariance, adjusted for baseline values on that measure using an intent-to-treat approach. Two-sided tests will be used with alpha at .05. With this sample size, power to detect a moderate effect size of 0.6 will be 80%, assuming equal standard deviations in the groups. The assumptions we are making to estimate power are conservative as evidenced by recent published tests of a parent mediated intervention for autism (Rogers et al., 2012) and a randomized controlled trial of a drug in FXS (Berry-Kravis et al., 2012), with samples sizes of 98 and 60, respectively, and behavioral outcome measures.

Analysis of our secondary outcome measure, the social avoidance subscale of the FXS- normed ABC, as well as the exploratory VAS and CGI will follow the same approach as the primary analysis. Additional analyses will examine potential child moderators of response to lovastatin (age, Leiter, ADOS symptom severity) using linear regression.

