Aim 1. Hypothesis 1b. We will use linear regression to test the relationships between parent behaviors and child outcome at 20 weeks (i.e., spoken language composite). The regression will include main effect terms for both treatment and parent behavior as well as the interaction term, while controlling for baseline values of the parent and child measures. Various parent confounders will be

evaluated as well (e.g., SCL-90-R severity score). The main effect of the parent behavior will test the contribution of PILI, whereas the interaction term will test the value of the combined treatment. These analyses will be done separately with two parent behavior measures (parent verbal responsiveness composite and quality of caregiver involvement score).

Analyses will be repeated for secondary outcome measures.

Aim 2. In the addressing hypotheses 2a, b, and c, we will identify biomarkers associated with FXS using a regression model for marker expression with grouping of phenotype (i.e., disease state or respond to treatment) as a predictor with important clinical cofounders as covariates. The marker performance will be evaluated using receiver operating characteristic (ROC) curves to test which biomarkers are statistically better diagnostic and prognostic tests for FXS. We will further develop predictive signatures of elements involved in MEK/ERK and Rho GTPase signaling pathways in response to lovastatin using PAM, or other pattern recognized methods. The potential biomarkers are phosphorylation of S6K1, AKt, EIF4E, and ERK/MEK as well as levels of IL-1, IL-6, IL- 10, MCP-1, IL-1alpha, IL-1beta, MMP-9, and MIF.

Based on the findings of [name] et al. (2016, American Journal on Intellectual and Developmental Disabilities) statistical power for this study is expected to be sufficient with a subject enrollment of 50. In the [name] study, a treatment effect was demonstrated with the same outcome measure and same age range in a sample size of 10 per group. In this multimodal study, it is expected that the effect of the drug, if it is to be clinically meaningful, will be at last as large as the effect of the language intervention by itself in the 2016 study. In fact, the expectation is to see expect synergistic effects with the language intervention amplifying the effect of the drug.

11) Procedures Involved

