Half of the participants will receive the Parent-Implemented Language Intervention (PILI) under consent form A, the remaining half of participants will have the option to participate in the clinical trial portion of the study under consent form B, at which point they will be guaranteed to receive the PILI intervention.

All participants will receive the Parent-Implemented Language Intervention (PILI) under the clinical trial portion of the study, consent form B. In addition to PILI, half of the patients will be randomized to take lovastatin and may experience a beneficial response to lovastatin including heightened response to PILI with language improvements and reduction of problematic behaviors of FXS including ADHD,

aggression, and anxiety. All participants under consent form B will also benefit by receiving physical exams, cognitive assessments, and blood tests.

18) Vulnerable Populations

The patient population to be studied is developmentally disabled children with fragile x syndrome. We have done research with developmentally disabled and cognitively impaired individuals of all ages for many years. The consent process for individuals without the cognitive ability to consent will be completed by the parent, caregiver, or legally authorized representative (LAR), and no procedures will be done with any subjects without consent of either subject or parent/caregiver/LAR.

19) Sharing of Results with Subjects

At the conclusion of the study, the possible medical benefit from the study will be reviewed with the subject and his or her parent/guardian. Any laboratory work considered standard of care will be available for patients at their request. Psychological assessment scores may be communicated to the subjects if it does not impact future testing. If a subject has to be unblinded for emergency purposes then the subject will be notified by the principal investigator or study physician. Unblinding will be conducted in accordance with the MIND Institute's SOP# 500-014: Study Subject Unblinding Process. The results of the study may also be published or presented at scientific meetings including peer reviewed scientific journals that will be made publicly available through PubMed Central. In addition, after publication the results will be posted on the MIND Institute website under clinical trials

20) Setting

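### The stated 80% power for an effect size of 0.6 does not follow from the inputs given: 25 per arm gives about 55%, and the planned ANCOVA reaches 80% only with an unstated baseline to week-20 correlation of about 0.67 or more

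*Combined protocol and SAP*

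**What the plan says.** Section 10 (Study Endpoints) makes the spoken language composite the primary outcome, measured at baseline and at the end of treatment. The groups are compared by "analysis of covariance, adjusted for baseline values on that measure using an intent-to-treat approach", with two-sided tests at 0.05. The power statement follows: "With this sample size, power to detect a moderate effect size of 0.6 will be 80%, assuming equal standard deviations in the groups". Equal SDs is the only assumption it names.

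Section 10 does not say what the sample size is. Section 4 does: "The final phase of the study (Phase3) will be a clinical trial (N=50" in total. Section 6 has "Consent form B will be utilized to enroll up to 50 subjects", and section 17 says "half of the patients will be randomized to take lovastatin". That makes 25 per arm.

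Two further pieces of text support the figure. Section 10 says "The assumptions we are making to estimate power are conservative" and points to two published trials, for which it gives only the sample sizes (98 and 60) and the type of outcome. The last paragraph of section 10 cites a 2016 study in which "a treatment effect was demonstrated with the same outcome measure and same age range in a sample size of 10 per group". It then carries this over to lovastatin: "it is expected that the effect of the drug, if it is to be clinically meaningful, will be at last as large". The yardstick for that expectation is what the PILI achieved alone in the earlier study.

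**The concern.** A two-group comparison of 25 against 25 at a standardized effect of 0.6 is well short of 80% power. Adjustment for baseline can make up the shortfall, but how much depends on how strongly the baseline composite predicts the week-20 composite, and the plan gives no value for that. It also leaves open whether 0.6 is in raw, change-score or baseline-adjusted SD units, and how many children are expected to contribute week-20 data.

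This is the only numerical power statement for the primary endpoint. A null result will be read as coming from a trial with a 20% chance of missing a 0.6 SD effect. Depending on inputs the plan does not state, that chance could be 20% or less, or it could be 33%, 43% or 45%.

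**Working it through.** **Inputs from the document.** N = 50, 1:1, so 25 per arm (sections 4, 6 and 17). Two-sided alpha 0.05, effect size d = 0.6, equal SDs, baseline-adjusted ANCOVA, stated power 80% (section 10).

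**Inputs not in the document, varied here as assumptions.** The baseline to week-20 correlation r, the SD scale of the 0.6, and the number analysed (50, 45 or 40).

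**Step 1: try to reproduce 80% from the printed inputs.** The noncentrality is d / sqrt(1/25 + 1/25) = 0.6 / 0.2828 = 2.121. With 48 df the two-sided 5% critical value is 2.011. Power from the noncentral t is 54.7%; the normal approximation gives 56.4%. Two-sided alpha of 0.10 gives only 67%. At d = 0.6, power is 79.5% with 44 per arm and 80.4% with 45. With 25 per arm, the effect detectable at 80% power is 0.81. The printed inputs therefore do not give 80%.

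**Step 2: credit the planned ANCOVA, with 0.6 in raw SD units.** Adjustment shrinks the residual SD by sqrt(1 − r²), so the working effect is 0.6 / sqrt(1 − r²), with N − 3 df.

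| r (assumed) | 50 analysed | 45 analysed | 40 analysed |
|---|---|---|---|
| 0 | 55% | 50% | 46% |
| 0.3 | 59% | – | – |
| 0.5 | 67% | 62% | 57% |
| 0.6 | 74% | – | – |
| 0.67 | 80% | 75% | 70% |
| 0.7 | 83% | – | – |
| 0.8 | 93% | – | – |
| r needed for 80% | 0.671 | 0.713 | 0.752 |

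Check at N = 50: sqrt(1 − 0.671²) = 0.741 and 0.6 / 0.741 = 0.81, the detectable effect from step 1. Simulated ANCOVA with random baselines (40,000 trials per value of r) gives 54.1% at r = 0, 66.1% at 0.5, 79.3% at 0.67 and 80.2% at 0.68, so the formula is optimistic by less than one point.

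Put the other way, the raw effect detectable with 80% power at N = 50 is 0.81 (r = 0), 0.77 (0.3), 0.70 (0.5), 0.65 (0.6) or 0.58 (0.7). The number per arm needed for 80% at 0.6 is 45, 41, 34, 29 or 24 for the same values of r.

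**Step 3: the other scales.**
- If 0.6 is already in baseline-adjusted SD units, the correlation has been spent. Power with 47 df is 54.7% whatever r is.
- If 0.6 is in change-score SD units, the ANCOVA effect is 0.6 × sqrt(2 / (1 + r)). Power is 84% at r = 0, 80% at 0.10, 73% at 0.3, 67% at 0.5 and 62% at 0.67. It reaches 80% only if r is 0.10 or less.

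**Step 4: does the supporting text supply what is missing?** For the trials of 98 and 60, no effect size, SD or correlation is given. Both are larger than this one, and a sample size alone does not show that assumptions are conservative. The 10-per-group study concerned the language intervention. Here every child receives that intervention and the contrast is lovastatin against placebo on top of it. The plan links the two by an expectation and prints no effect size.

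**The case against.** The strongest reply is that this is an omitted assumption, not a wrong calculation. The plan specifies ANCOVA in the same paragraph as the power sentence, and with 0.6 in raw SD units and r of about 0.67 the 80% is correct. The composite pools conversation and narration samples, and the alternate versions of the materials are counterbalanced (section 11(a), Child Spoken Language), so a correlation of that size cannot be ruled out. Retest data may also sit in the preliminary studies to which that section refers. All of this stands: the 80% is unsupported, not impossible. But the power sentence names equal SDs and is silent on r, the input that moves power from 55% to 93% between r = 0 and r = 0.8.

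A second reply is that the 10-per-group study implies a large effect. If its result was a two-sided p below 0.05 on a two-group comparison (an assumption), the observed effect was at least about 0.94, and a true effect of that size would have about 90% power at 25 per arm. That is a conditional bound on a different contrast, from a small sample in which a significant estimate may be inflated. It says nothing about power at 0.6.

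Third, losses may be small. Section 9 plans on 50 children, and section 15 asks those who stop drug early to return for a final visit. The 45 and 40 columns are illustrations. Even so, 50 is an upper limit in section 6, sections 11(b) and 15 describe ways children can leave before week 20, and no allowance is stated.

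**Conclusion.** The concern holds. On the inputs the plan prints, power at 0.6 is about 55%, some 25 points below the stated 80%. The planned ANCOVA reaches 80% only if 0.6 is in raw SD units and r is about 0.67 with complete follow-up, rising to 0.71 with 45 analysed and 0.75 with 40. At r = 0.5 the chance of missing a true 0.6 SD effect is 33% with 50 analysed and 43% with 40; with no gain from adjustment it is 45% with 50. These figures assume equal SDs and 1:1 allocation, and the values of r and the reduced numbers are assumptions shown as a range. If the sponsor did assume a correlation of about 0.67 or more on the raw scale, the 80% can stand once that is printed. As written, the figure cannot be checked, and it should be corrected before the trial is interpreted.

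**What to change.** Replace the power sentence in section 10 with wording such as:

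> With 25 per arm and two-sided alpha 0.05, power for an effect size of 0.6 is about 55% before baseline adjustment. Power of 80% corresponds to an effect size of about 0.81, or to 0.6 in raw SD units if the baseline to week-20 correlation is about 0.67 with complete follow-up (0.71 with 45 analysed, 0.75 with 40).

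Then:
- State the SD scale of the 0.6, the correlation and its source, and the number expected to be analysed. If a correlation lay behind the 80%, print it.
- Show power over a range of correlations, not at one value. Phase 2 can inform the range but not settle it: with at most 30 children, an observed r of 0.67 has a 95% interval (Fisher z) of about 0.41 to 0.83, which corresponds to power of 62% to 96%.
- Remove the claim that the assumptions are conservative.
- Keep the 10-per-group paragraph as rationale, not as a power calculation.

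The cost is wording only. No patients are added, and the test, alpha and allocation stay as they are. The stated power becomes less favourable or openly conditional; actual power is unchanged.

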i. The Clinical Global Impressions Scale–Severity (CGI-S) and Improvement (CGI-I) (Busner & Targum, 2007): ICF B

These standardized assessment instruments are widely used in drug trials to enable the clinician to utilize history from the parents or caregiver and incorporate it into a clinical rating, first for severity, and then for clinical follow-up. The CGI-S will be used at the pre-treatment assessment to judge symptom severity and the CGI- I will be used at the 3 month and 6 month visits.

ii. The Visual Analogue Scale (VAS): ICF B

The measure will be used to assess parental impressions of progress in two key symptoms: spoken language impairment and social impairment. The distance of the mark from one end is used as the outcome variable for analysis. The VAS will be administered at each visit. The VAS has been effectively used as an outcome measure in other FXS drug trials (Erickson et al., 2011; Paribello et al., 2010; [name] et al 2013).

11 (b). Medical/Safety Assessments (Consent Form B):

The schedule of procedures is also listed in a table format below:

Assessment	Screening/Baseline Visit 1 (Week 1, Day 0)	Visit 2 (Week 10 ± 3 Days)	Visit 3 (Week 20 ± 3 Days)	
Informed Consent	X			
Inclusion/Exclusion Criteria	X			
Medical History	X			
Vital Signs	X	X	X	
Physical Exam	X	X	X	
Neurological Exam	X	X	X	

For IRB Use

Document Revision Date: July 12, 2013

Concomitant Medications	X	X	X
Adverse Events	X	X	X
Clinical Labs	X	X	X
Biomarkers	X	X	X
Leiter-R (45 min.)	X		
ADOS-2 (45 min.)	X		
CGI-S	X		
CGI-I		X	X
VAS	X	X	X
Language Assessments			
CELF-4 (15 min.)	X		X
CASL (45 min.)	X		X
TROG-2 (10 min.)	X		X
PPVT-4 (10 min.)	X		X
EVT-2 (10 min.)	X		X
FACB (45 min.)	X		
Child Spoken Language (30 min.)	X		X
Parent Narrative Task 1 (15 min.)	X		X
Parent Narrative Task 2 (15 min.)	X		X
Parental Assessments			
K-BIT-2 (maternal) (25 min.)	X		
Parent Questionnaires			
ABC (15 min.)	X	X	X
ADAMS (10 min.)	X	X	X
RBS-R (10 min.)	X	X	X
PSI (10 min.)	X		X
PSOC (10 min.)	X		X
Family Background	X		
Questionnaire (10 min.)			
SCL-90 (maternal) (10 min.)	X		X
Post Treatment Survey			X
Dispense Medication	X	X	

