Randomization to lovastatin or placebo will be conducted by the UCDMC pharmacy using a computer algorithm. IDS will over-encapsulate the active study medications and prepare the placebo capsules prior to dispensing. Equivalence of the groups on these stratification variables, as well as other variables (e.g., child autism symptom severity and maternal IQ), will be tested, with any significant differences accounted for by inclusion of covariates in the primary analyses.

The dose will range from 10 to 40 mg of lovastatin or placebo depending on tolerance of the dose. The dose will start at 10 mg per day and will be increased by 10 mg increments on a weekly basis from study weeks 1 through 4 as listed below. Dosing will occur once per day in the evening. Dose tolerance will be assessed through a weekly phone call or email contact conducted by a study physician during the titration period and a dose decrease can be made if necessary. If a dose decrease is made between weeks 2 and 4 no further dose titrations will occur and subject will be considered on a stable dose throughout the remainder of the titration period and study.

If more than one dose change is needed, the subject will be discontinued from the study. Once a stable dose is reached, subjects will remain at the designated dose through visit 3 and will be contacted approximately every other week by study staff to assess for possible adverse events and verification of proper dosing. Study participants will be dispensed study medication at visits one and two and will discontinue dosing after completing visit 3.

Week 1: 10 mg (Day 1-7) Week 2: 20 mg (Day 8-14) Week 3: 30 mg (Day 15-21) Week 4: 40 mg (Day 22- 28) Week 5-20: 40 mg or OTD (Day 29- 140)

Our dosage model takes into consideration the biphasic and pleiotropic effects of statins. The biphasic effect can be explained by the higher affinity for the enzymes that catalyze non-sterol product formation than for the cholesterol biosynthesis enzymes. Low doses of statins mainly affect cholesterol synthesis, while high doses affect mevalonate-derivative intermediates, which are essential for the prenylation of proteins and Ras activation (Li, et al., 2007). The pleiotropic effects of statins suggest that the sustained use of statins (more than 2 weeks) causes PTEN up regulation, which inhibits the PIK3/AKT pathway; and that higher acute dose administration of statins will inhibit Ras, which is our targeted effect. (Ludman, et al., 2009).

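### ABC social avoidance and VAS are collected at Week 10, but their stated end-of-treatment ANCOVA gives that value no role and no missing-data rule is stated

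*Combined protocol and SAP*

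**What the plan says.** Section 10 (Study Endpoints) defines the primary outcome at two time points: "The primary outcome measure is a spoken language composite measured at baseline and at the end of treatment". The arms are compared by analysis of covariance adjusted for the baseline value, under an intent-to-treat label. The same section then says that the social avoidance subscale of the ABC, the VAS and the CGI "will follow the same approach as the primary analysis".

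The schedule in section 11(b) marks the ABC and the VAS at Visit 1 (baseline), Visit 2 (Week 10) and Visit 3 (Week 20). Section 11(a) confirms this for one of them: "The VAS will be administered at each visit". The child spoken language samples behind the primary composite are marked at baseline and Week 20 only.

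Three other places bear on who has a Week 20 value:
- The dosing text in section 11(b): "If more than one dose change is needed, the subject will be discontinued from the study".
- Section 11(b) also stops the medication on signs of myopathy, muscle pain or allergic reaction.
- Section 15 asks children who stop drug early to attend a completion or early termination visit. Follow-up assessments there are optional and not listed. After consent is withdrawn there is no follow-up.

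The documents contain no repeated-measures model, imputation or carry-forward rule, expected dropout rate, or definition of the intent-to-treat set.

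**The concern.** A method suited to an outcome measured twice has been carried over to outcomes measured three times. The middle measurement then does nothing in the analysis. For a child who leaves between Week 10 and Week 20, the Week 10 score is the best available predictor of the missing value, and the stated model cannot use it.

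Two things are at stake for the secondary behaviour endpoint. One is precision: the child's information is lost. The other is bias: if children who are doing badly at Week 10 leave more often on one arm, the Week 20 comparison among those remaining flatters that arm.

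**Working it through.** **The plan's own figure.** The only numerical claim is for the primary endpoint: "power to detect a moderate effect size of 0.6 will be 80%, assuming equal standard deviations in the groups". With 50 children allocated 1:1 (sections 9 and 17) and two-sided 0.05, the normal approximation gives Φ(0.6 × √(25/2) − 1.96) = Φ(0.161) = 56.4%. ANCOVA gets close to 80% only with a baseline correlation near 0.65 (79.7%), which is not stated. That is a separate matter. No power is claimed for ABC or VAS, so there is no figure to reproduce for this point.

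**Assumptions for what follows.** None of these is in the documents: baseline correlation 0.6 with each later visit, Week 10 to Week 20 correlation 0.6 to 0.8, normal scores with SD 1, 25 children per arm, and true effect zero unless stated.

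**Step 1: precision under random dropout.** Let f be the fraction lost after Week 10 and p the Week 10 to Week 20 correlation given baseline.
- p = (r − 0.36)/(1 − 0.36), which is 0.24/0.64 = 0.375 at r = 0.6 and 0.44/0.64 = 0.6875 at r = 0.8.
- Variance per arm is s²/[n(1 − f)] for the ANCOVA and s²[(1 − p²)/(1 − f) + p²]/n for a likelihood model that uses Week 10. Their ratio is 1 − f·p².
- At f = 0.1 the saving is 0.1 × 0.141 = 1.4% to 0.1 × 0.473 = 4.7%. At f = 0.2 it is 2.8% to 9.5%.

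So the saving is 0 to 10%. In power terms, over 10 to 30% loss and the correlations tried (baseline 0.5 or 0.65, Week 10 to 20 from 0.5 to 0.8), the gain for an effect of 0.6 is 0.5 to 6 points.

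**Step 2: differential dropout alone.** Losing 40% of the drug arm at random and nobody on placebo gave a simulated ANCOVA bias of 0.001 SD. When the worst baseline scorers left instead, it was 0.004 SD. Neither is a problem, because the model adjusts for baseline.

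**Step 3: dropout that depends on the Week 10 score (4000 simulated trials per setting).**

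| Who leaves after Week 10 | ANCOVA bias (SD) |
|---|---|
| Graded dependence in the drug arm | about 0.03 to 0.07 |
| Worst-scoring 20% of drug arm (10% of sample), no placebo loss | 0.09 to 0.16 |
| Worst-scoring 40% of drug arm (20% of sample), no placebo loss | 0.16 to 0.30 |

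The graded result depends on how steep the dependence is. With 10% placebo loss and about 20% drug loss, log-odds slopes of 0.3 to 0.7 per SD gave 0.015 to 0.04. A steeper slope of 1.2 (baseline correlation 0.5, Week 10 to 20 correlation 0.7, 25% drug loss) gave 0.11. For scale, with 10% placebo and 20% drug loss the standard error is √[0.64 × (1/22.5 + 1/20)] = 0.25 SD.

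**Step 4: hand check of the adverse rows.** Removing the lowest 20% of a normal distribution raises the mean of the rest by 0.280/0.8 = 0.35 SD. The part not explained by baseline is 0.64 × 0.35 = 0.224. Multiplying by p gives 0.08 to 0.15. For the lowest 40%: 0.386/0.6 = 0.644, then 0.64 × 0.644 = 0.412, giving 0.15 to 0.28. This approximation ignores the change in the baseline slope after truncation and lands just below the simulated values.

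**Step 5: the repeated-measures estimate.** In the same simulations it was within 0.01 SD of zero. That is by construction, since dropout was generated from observed scores. In the adverse case with the weaker correlation its variance rose by up to about 7%.

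**The case against.** The strongest reply has four parts.

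- **The plan does not say completers only.** A reader might infer that the plan, as a rule, discards Week 10 and drops these children from an intent-to-treat analysis. The documents do not state that. It follows only from a model with no place for Week 10 plus the absence of any missing-data rule. For a child who stops drug early, the section 15 visit could count as end of treatment and supply a score. This stands as a softening. It does not close the gap, because the assessments there are optional, ABC and VAS are not named, and nothing says how such a value would be used.
- **Unequal dropout is not bias.** A reader might infer that tolerability-related loss, being likely to differ by arm, biases the ANCOVA. Step 2 shows that it does not. Leaving must also track the post-baseline score, and nothing in the documents ties statin intolerance to social avoidance. This stands in full.
- **The dose-change rule acts mostly too early.** It sits in the titration text for weeks 1 to 4, before any Week 10 score exists, and a child lost then gains nothing from the proposed model. This largely stands. Later exits remain possible through muscle symptoms, Week 10 safety laboratory results, non-compliance or consent withdrawal. Stopping the medication, however, need not end follow-up.
- **The large bias figures come from an extreme case.** They do: all the loss is on drug, and it is exactly the worst scorers. They are an upper illustration, not a forecast.

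**Conclusion.** The point holds as a limited one. For ABC social avoidance and the VAS, a scheduled Week 10 measurement has no role in the stated analysis. A child without a later score has no outcome in the model unless the early termination visit provides one. The ANCOVA may be biased if leaving after Week 10 depends on the Week 10 score: about 0.03 to 0.07 SD with graded dependence, and 0.09 to 0.30 SD only when the worst-scoring 20 to 40% of the drug arm leave and no placebo child does. If dropout is random, what is lost is 0 to 10% in variance. All these sizes rest on assumed dropout and correlations.

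The point does not reach the primary conclusion. The language composite has no Week 10 measurement, so the remedy cannot help it, although it too lacks a missing-data rule. The CGI-I is also collected at Week 10 and named in the same sentence of section 10. It is not covered here because it is a change rating with no baseline value of its own. This is a cheap improvement, not a flaw that threatens the trial.

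**What to change.** For ABC social avoidance and the VAS, specify a mixed model for repeated measures:
- outcomes: Weeks 10 and 20;
- fixed effects: arm, visit, arm-by-visit, baseline and baseline-by-visit;
- unstructured covariance;
- test: the Week 20 arm contrast.

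Keep the ANCOVA as a sensitivity analysis. State in the same paragraph which children form the intent-to-treat set, and whether ABC and VAS scores from an early termination visit are used and at which time point.

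The cost is a few lines of plan and code, with no new data. With two post-baseline visits the unstructured covariance has three parameters, a modest load for 50 children. With complete data the Week 20 estimate equals the ANCOVA's. The change is not free: it relies on missingness being explained by observed data, can slightly raise the variance in adverse settings, and does nothing for children lost before Week 10. A sensitivity analysis for data not missing at random would show how far the first of these matters.
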